8.9 Special Information Excluded during Hypothesis Testing and Justification (If Applicable)

Not applicable.

9. Data Management

Data management will be done by the Sponsor or the delegated Contract Research Organization (CRO) according to the SOP of data management. The data management process includes the establishment of capture/management system, design of CRF and database, data receiving and entry, data check and query, medical coding, external data management, Blind Review, Database Lock, data export and transmission, filing of data and data management documents, etc.

The data management plan should specify the database locking process, person in charge and SOP document executed. Unlocking and re-locking after database lock should be pre-defined with the conditions and processes specified. The data management plan should specify trial data to be archived, management file, media, and way and time limit of archiving.

10. Feasibility Analysis

10.1 Feasibility analysis of success

As stated above, the devices in the control group are surgical sutures that have been extensively applied in clinical practice, while the investigational products are suture devices that have brand new designs and have only been marketed in the US for one year; however, their main design elements, cutting knotless^[1-5] and antimicrobial (triclosan)-coating^[11,12] are mature and validated techniques. In the meantime, thyroid surgery incision is a clean incision, for which intradermic continuous suture is already a standard closure pattern. Therefore, it is likely to

achieve the noninferiority goal in the protocol and appropriate to expect success rates of 98% in all treatment groups.

In addition, according to the inclusion/exclusion criteria in the protocol, a large number of subjects can be included while the devices used in the study are supplied free of charge and hence will not increase the subjects' burden, making it less difficult to enroll and screen subjects.

To sum up, the likelihood of success in this study is relatively high.

10.2 Feasibility analysis of failure

As stated above, the investigational products are the combination of two mature techniques, but they have only been marketed in the US for one year and have not been reported in any related clinical literature yet. There may be some undiscovered problems that can cause some unforeseen problems in this study.

In addition, in this study, subjects are required to go back to hospital for follow-up visits 1-2 times at most after their surgery and discharged, which may make some subjects lost to follow-up. This may not be completely avoided under the condition that subjects are fully informed. According to the requirements of this study, lost-to-follow up and withdrawn subjects should be controlled within 10% of all the subjects.

To sum up, although the study may fail for some reasons, the overall likelihood is relatively small.

11. Quality Control of Clinical Trials

During the clinical study, the Sponsor and Investigator should execute their respective responsibilities according to the Good Clinical Practice for Medical Device Trials and applicable related Chinese and international regulations. They should also strictly follow the clinical trial protocol to ensure the quality of clinical trial.

The Sponsor will ensure proper training on the clinical trial protocol and the use and maintenance of investigational medical device for all investigators participating in the trial, to ensure the consistency in the implementation of clinical trial protocol, the use of investigational medical device.

During the implementation of study, the Sponsor is responsible for monitoring each phase of the clinical trial. The clinical monitor employed by the Sponsor or appointed representative should comply with the related standard operating procedure (SOP) and clinical trial protocol that are established by the Sponsor to monitor the clinical trial, to ensure the complete, accurate, true and reliable data.

To ensure the quality of study, the Sponsor may authorize the eligible auditor to audit the clinical trial, as needed. The Investigator should allow the auditors to review the original data and documents related to this study after receiving the notification.

When the Food and Drug Administration, Health Planning Department or other regulatory agencies send the inspection personnel to carry out the inspection, the clinical trial institution and Investigator should cooperate and immediately notify the Sponsor.

12. Clinical Trial-Involved Ethical Issues and Informed Consent

12.1 Ethical Concerns

CONFIDENTIAL

Ethical issues involved in this study have been stipulated according to China's laws and regulations and international consensus such as the Declaration of Helsinki, the protocol design has taken ethical principles into full consideration, and the rights, safety and health of trial subjects are the most important concerns. The specific contents should at least include:

- 1) Regulations to make sure subjects are fully informed
- 2) Regulations that respect and protect subjects' privacy, and that keep records possibly identifying subjects confidential
- 3) The production of investigational product should meet the relevant requirements of applicable quality management system for medical devices; the processing and storage of investigational product should meet the requirements of IFU and SOP. The investigational product should be used according to the approved protocol and related operation instructions. The reference product should be used to ensure the safety of subjects to the maximum extent.
- 4) Qualified clinical study sites and investigators should be selected, and investigators should make medical decisions that are in the best interest of subjects
- 5) In the inclusion/exclusion criteria of the study, inclusion criteria for subjects of different groups should be identical; subjects who withdraw from the study will not affect the treatment of disease; Subjects who suffer from study-related injury will be given appropriate treatment and compensation (see ICF)
- 6) Before any subject is recruited, the study protocol and its amendments, ICF and other study-related documents applicable must be submitted to the corresponding EC for review and must obtain written comments from the EC.

12.2 Approval of Trial Protocol

The trial protocol should be internally approved and filed according to the company's SOP prior to submitting to the external agency (including but not limited to the government regulatory agencies, Ethics Committee).

The clinical trial protocol should not be implemented until the written approval is obtained from the Ethics Committee according to the relevant requirements of laws and regulations.

12.3 Process of Informed Consent and Text of Informed Consent Form

12.3.1 Process of informed consent

The informed consent of all subjects participating in the study must be obtained prior to performing any study tests/procedures. The Investigator must explain the background of the study presented and the benefits and risks of surgery and study to the subjects before the subject participates in the study. Only the subject who signs the latest informed consent form that is approved by the EC prior to participating in the study is eligible to participate in this study. Subject who has not signed the written ICF is not eligible to participate in this study.

Each subject (or legally authorized representative) must sign and date the latest informed consent form that is approved by the EC prior to implementing any study-related items or operations not belonging to the standard treatment and after the nature of this study is fully clarified.

The process of obtaining the written informed consent needs to prove that the subjects volunteer to participate in this study. All aspects of this study must be clarified to the subjects prior to signing the informed consent form, and questions raised by the subject must be clearly answered. The Investigator and/or designee must clearly document the process of obtaining informed consent in the subject clinical record. The investigator has responsibilities to ensure the process of obtaining the informed consent is implemented according to the Good Clinical Practice for Medical Device Trials and related regulations, such as ISO 14155, the Declaration of Helsinki.

See ICF.

13. Device Management

In this study, the Sponsor will provide all the study products and control products. The packages of the products should be clearly specified with “For Clinical Trial Only”.

13.1 Accountability of investigational devices

All the study involved devices received must be counted, of which the quantity should be checked continuously throughout the study: the investigator and/trained designated person should record the receipt, use, dispensing and return of devices during the study properly. These investigational devices must be kept in a secure location with restricted access and stored according to the conditions outlined in the IFU. In all circumstances, the investigational device is intended for use by the investigator or sub-investigator for subjects consented for participation in this clinical study only.

An accountability log will be used by each site to acknowledge receipt of all investigational devices and to record the disposition of all investigational devices on an ongoing basis throughout the course of the study. The process of device accountability and checking should be thoroughly explained during the study site initiation period. The responsible monitor will review the investigational device accountability at each monitoring visit.

In addition, the following but not limited paper study documents must be maintained as well:

- Each subject’s product accountability tables of implanted device (this may include the original document and/or packaging label of the investigational/control product used);
- All forms documenting the investigational devices return process;
- All forms related to transport and receipt of investigational devices.

13.2 Return of investigational devices

All unopened and unused (e.g., expired), opened and unused, damaged, mislabeled or malfunctioning investigational devices must be returned to the Sponsor with related form. During the study site initiation visit, the Sponsor should train the investigator thoroughly.

14. Regulations of Adverse Event and Device Complaint Reporting

14.1 Adverse Event

AE is an untoward medical occurrence during the clinical study and which does not necessarily have a causal relationship with the study medical device.

Ever since the randomization of subjects, the investigator must confirm if any AE occurs, and if any, determine the relationship between AE and investigational device or surgical procedure, when evaluating subjects enrolled by clinical study each time.

Postoperative fever, postoperative pain, incisional scar formation and laboratory abnormalities are expected to occur after surgery and will not be recorded as AE in this study, unless the investigator believes the degree of pain or fever exceeds the subject’s normal expected range after surgery or related to study devices.

Other AEs, investigational device failure and other product problems must record in the medical record and entered the e-CRF.

The severity of AE will be separated into the following grades:

Mild: Awareness of sign or symptom that does not interfere with the subject's usual activity or is transient, resolved without treatment and with no sequelae,

Moderate: Interferes, but does not hinder, the subject's usual activity and may require treatment;

Severe: Causes severe discomforts, results in major impact on the subject's activities of daily living and requires treatment or intervention.

The causal relationship should be assessed as follows:

Unrelated	There is no correlation between the AE and the use of medical device
Possibly unrelated	The occurrence of AE is more likely to be associated with other factors, e.g.: concomitant medication or concomitant disease, or the occurrence time of the event does not suggest a causal relationship with the use of study-related device.
Possible:	The occurrence of AE may be caused by study-related device. Other factors may have contributed to the event, e.g.: concomitant medication or concomitant disease. The event occurs within a reasonable time after the use of study-related device and the causal relationship between the event and the use of study-related device cannot be ruled out.
Probable	The occurrence of AE is probably caused by the use of study-related device. The event occurs within a reasonable time after the use of study-related device, e.g.: it is confirmed after the medical device is taken out. It is unlikely to have another explanation for the event (e.g. concomitant medication or concomitant disease).
Definitely Related:	The occurrence of AE has been confirmed as a definite side effect of the medical device and cannot be explained by other reasons (e.g. concomitant medication and concomitant disease). The occurrence time of the event highly suggest a causal relationship (e.g. reaction after removal of medical device and replantation of medical device).

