7.1.3 Measures to Reduce and Avoid Bias

In the study, central randomization will be adopted to randomly assign eligible subjects to one of the three groups: investigational group 1, investigational group 2 or control group according to the same inclusion/exclusion criteria to reduce the impact caused by unknown confounding factors and avoid selection bias.

Study blinding is as follows:

- Subject: Subjects are informed prior to surgery that they will be randomized to any of the study groups with equal probability, and during the surgery, a blinding method will be adopted for them.
- Investigator responsible for incision suture: Considering the investigational groups and

[PROTOCOL VERISON AND DATE] V2.0/2019-09-30

control group use different shapes and usages of suture, it is impossible to blind investigators who are responsible for suturing.

- Central evaluator: Imaging data will be submitted to Imaging Center for assessment to assess the primary endpoint and the modified Hollander score among secondary endpoints. The Central Imaging evaluators will be blinded.
- Monitor: As the product information is specified on the detachable label supplied with the product and instrument counting and source document verification is - done with the study product inventory records and subject's medical record, the monitor will not be blinded.

In addition, this study will collect data about objective measures, study related information will be recorded in the source medical records as detailed as possible, the monitor will pay attention to verifying the data in the source medical records during the monitoring process, investigator training will be strengthened, and investigators will closely communicate with subjects to improve compliance of subjects. This will help to reduce the informational bias.

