14.2 Serious Adverse Event

SAE refers to any untoward medical occurrence in a clinical trial that results in death or serious deterioration of health status, including life-threatening conditions or damage, permanent defect of body structure or body function, events requiring inpatient hospitalization or prolongation of existing hospitalization, those requiring medical or surgical intervention to avoid permanent defect of body structure or body function; and those resulting in fetal distress, fetal death or congenital anomaly/birth defect, etc.

A planned hospitalization and/or medical intervention for pre-existing conditions, or a procedure required by the protocol, without serious deterioration in health, is not considered to be a serious adverse event.

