14.5 Reporting Procedure and Contact Person Information

The investigator should ensure sufficient treatment is given for any AE experienced by a subject, including clinically significant laboratory test values related to this study.

Once a subject is randomized, his/her AE should be followed up, until they are resolved or stabilized and the clinical outcome has been determined, or until his/her last follow-up visit (the earliest one shall prevail). If the investigator considers the AE is related to the study product, the subject must be followed up until the event is resolved and stabilized.

The investigator must report the AE to the Sponsor via e-CRF within 2 weeks after its awareness. The Investigator should record the nature, severity, treatment and outcome of AE and determine whether the AE is related to the study device, medication, or surgical procedure defined in the study protocol or not.

All the SAEs must be followed up until they are resolved (with or without sequela). When the event is not resolved or stable at the end of study, the medical monitor in this clinical study will decide whether it is necessary to collect the further follow-up information. The Investigator should send a report to regulatory agencies at different levels, EC and the Sponsor within 24 hours after the awareness of a SAE.

The Investigator must report any SAEs and any device defects possibly leading to SAE that occur during the study to the Sponsor and related regulatory department required by laws and regulation within 24 hours after the awareness of the event or defect; and provide further information upon the sponsor's request.

For any SAE and device defect that may lead to SAE, the Investigator should report it to the regulatory authorities, EC and the Sponsor within the time limit defined by the Sponsor. According to the requirements of No.25 Decree, the Sponsor should report the SAE or defect to the Food and Drug Administration Department and Competent Department of Health and Family Planning at the same level within 5 working days after its awareness. – The Sponsor will notify other clinical trial institutions and investigators participating in the trial and notify the EC of the clinical trial institution involved in a timely manner via its medical device clinical trial management department.

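### The adverse-event exemption in Protocol 14.1 readmits scar and laboratory events only if judged device-related, which conflicts with 14.5 and may not cover the control sutures

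*Protocol*

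**What the plan says.** Protocol 14.1 first defines an adverse event without requiring a causal link to the device. It then exempts four event types: "Postoperative fever, postoperative pain, incisional scar formation and laboratory abnormalities are expected to occur after surgery and will not be recorded as AE". The exception has two limbs. The first is degree: "unless the investigator believes the degree of pain or fever exceeds" what is expected for that subject. The second is relatedness, which closes the same sentence: "normal expected range after surgery or related to study devices".

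Three other places bear on the rule.

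- **Protocol 14.5** asks the investigator to ensure treatment for any adverse event, "including clinically significant laboratory test values related to this study". It also sets the serious-event duty: "The Investigator must report any SAEs and any device defects possibly leading to SAE that occur during the study to the Sponsor", within 24 hours.
- **Protocol 14.2** defines a serious event without reference to 14.1: "SAE refers to any untoward medical occurrence in a clinical trial that results in death or serious deterioration of health status". The definition includes "events requiring inpatient hospitalization or prolongation of existing hospitalization".
- **Protocol 7.1.3** says of the surgeons that "it is impossible to blind investigators who are responsible for suturing". No blinded assessor of adverse events is named anywhere.

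SAP 14 summarises adverse events by arm, including by relationship to the device. SAP 14.1.2 takes serious events from the adverse-event page of the eCRF. Protocol 8.1 rules out inferential statistics for safety.

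**The concern.** For scar formation and laboratory abnormalities, the rule makes causality a condition of entry. The SAP then tabulates relationship from unrelated to definitely related, but for these two types the unrelated events never reach the table.

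This matters because of what the trial is for. Protocol 4.3 says the design is meant to show that barbs do no harm to safety or efficacy, and the safety side of that rests on recorded counts by arm. Scar is not a side issue either: Protocol 4.1 gives scar reduction as a reason for the choice of suture technique and material, and exclusion criterion 11 keeps out subjects with a keloid history. If entry depends on attribution, and attribution can depend on knowing the arm, arms with the same true rate can show different recorded rates.

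**Working it through.** The check is a reading of passages against each other; the plan gives no figure to reproduce.

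**1. Which limb reaches which event (14.1).**

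| Event type | Returns by degree | Returns by relatedness |
|---|---|---|
| Fever | yes | yes |
| Pain | yes | yes |
| Scar formation | not named | yes |
| Laboratory abnormality | not named | yes |

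The relatedness limb has no subject of its own in the sentence. The table takes the wider reading, that it applies to all four types. If it applied only to pain and fever, scar and laboratory events would have no route back at all.

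**2. Against the definition in 14.1.** The definition says causality is not needed. The last column says that for two event types it is.

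**3. Against 14.5.** Section 14.5 treats clinically significant laboratory values connected with the study as a kind of adverse event. Section 14.1 keeps laboratory abnormalities out however marked, unless device-related. Connection with the study is not the same condition as relation to a device, so a site cannot apply both texts to the same result.

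**4. Who attributes.** Section 7.1.3 leaves the suturing investigators unblinded. The documents do not say who assesses adverse events at the Day 5-7 and Day 28-35 visits. The assessor may therefore know the arm; the text neither requires nor prevents it.

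**5. What study devices covers.** In the closure procedure of 7.2.3, the investigational sutures are called the study device and the comparators the control device. The Study Device row of the synopsis describes only the two barbed sutures. Yet the heading of that closure procedure uses study products for all three arms, and the withdrawal visit uses study sutures for any randomised subject. Usage does not settle the meaning in 14.1.

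**6. Precedence over serious events.** Section 14.1 has no clause yielding to 14.2. Sections 14.2 and 14.5 stand on their own terms and make no exception for the four types. SAP 14.1.2 counts serious events from the adverse-event page, so an event kept off that page under 14.1 would be reportable but would have no stated path into the SAP table.

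**7. Size.** Let r be the true rate of such events, the same in both arms, and let a_T and a_C be the probabilities that one is attributed to the suture in a test arm and in control. The recorded gap is r × (a_T − a_C). It is zero when attribution is even-handed and can take either sign. If the exception were read as excluding control sutures, a_C would be 0 for these two types. The documents give none of r, a_T or a_C, so no number follows.

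**The case against.** The strongest reply is that little is lost in practice.

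- **Scar.** The exemption is for what is expected after surgery, so a pathological scar may fall outside it. Blinded evaluators also score Day 28-35 photographs in every arm with the modified Hollander scale, and wound complications are collected at both follow-up visits on an open-ended list with no attribution condition. This stands in part. The scale in Annex 3 has contour and overall-appearance items but none for a raised scar, and a cosmetic score is not an adverse-event record. Section 14.1 sets no limit of degree for scar as it does for pain and fever.
- **Laboratory values.** The schedule in 7.2.1 has only glucose and pregnancy tests, both at screening, while adverse events are collected from randomisation. Only results from routine care are affected, and the 14.5 sentence is about ensuring treatment. This limits the reach of the contradiction but does not remove it.
- **Terminology.** SAP 14 tabulates relationship to the study device by arm without leaving out control. This shows the likely intent; the definition is still missing.

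A reader might also infer more than the text supports:

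- **That all four event types need a device link.** Fever and pain do not; excess degree is enough.
- **That serious events go unrecorded.** Sections 14.2 and 14.5 require every serious event to be reported, whatever 14.1 says. Fever that prolongs a hospital stay would ordinarily exceed the expected range as well.
- **That wound events in general are filtered by attribution.** Infection, separation or dehiscence, and delayed healing are separate safety endpoints, and pain has its own scale completed by blinded subjects.

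**Conclusion.** The point holds for two event types. On the literal text, an abnormal scar or a clinically significant laboratory abnormality that the investigator judges unrelated to study devices is not recorded as an adverse event. That contradicts the definition in 14.1 and conflicts with 14.5. Recording of these two types can differ by arm, because the investigator who makes the attribution may know the arm and because the exception may be read as not covering the control sutures. This is a risk and not a demonstrated bias, and neither its direction nor its size can be derived.

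On serious events the finding is unclear precedence between 14.1 and 14.2, together with a SAP table drawn from a single eCRF page. It is not a shown loss of events.

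The primary endpoint, sample size and decision rule are untouched. Because safety is descriptive only, no test is affected, but the recorded counts are then themselves the evidence. The conclusion assumes that sites follow 14.1 as written and that no CRF guidance outside these documents already resolves it.

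**What to change.** Amend the exemption paragraph in Protocol 14.1 to do four things:

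1. Limit the exemption, for all four types, to findings within the expected postoperative course.
2. State that it never applies to an event meeting 14.2, and that every such event is entered on the adverse-event page from which SAP 14.1.2 draws its table.
3. Record clinically significant laboratory abnormalities and abnormal scars in all arms whatever the attribution, and align the wording of 14.1 and 14.5 on laboratory values.
4. Define study devices to include the control sutures, and use the term in that sense in 14.1 and SAP 14.

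The cost is one amended paragraph with matching CRF guidance, a few more adverse-event entries, and a slightly higher reported rate in every arm.
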